14.8. Appendix 8: Values of Potential Clinical Importance

14.8.1. Laboratory Values

Reference ranges for all laboratory parameters collected throughout the study are provided by the laboratory. A laboratory value that is outside the reference range is considered either high abnormal (value above the upper limit of the reference range) or low abnormal (value below the lower limit of the reference range). Note: a high abnormal or low abnormal laboratory value is not necessarily of clinical concern. The laboratory reference ranges will be provided on the listings of laboratory data. Clinical laboratory test results outside of the reference range will be flagged in the listings.

To identify laboratory values of potential clinical importance, National Cancer Institute Common Terminology Criteria for Adverse Events (NCI-CTCAE v5.0) will be used to assign grades to the relevant laboratory parameters. NCI-CTCAE v5.0 can be found at <http://ctep.cancer.gov/reporting/ctc.html>.

For laboratory data which are not listed in the NCI CTCAE v5.0, a summary of values outside the normal range will be provided.

14.8.2. ECG Parameters and Vital Signs

For ECG and vital signs, outputs per the most updated IDSL standard up to the RAP effective date will be provided.

Unless otherwise specified, ECG displays will be based on central reading.

14.9. Appendix 9: Pharmacokinetic / Pharmacodynamic Analyses

14.9.1. Pharmacokinetic / Pharmacodynamic Dataset Specification

If deemed appropriate and if data permit, dose/exposure - objective response relationships between belantamab mafodotin dose/exposure and clinical activity may be explored based on pooled data from Study 208465 and overseas studies using population methods. Dose/exposure will be assessed based on dose intensity, duration of exposure in days, Cmax and AUC. Clinical activity will be assessed based on objective response which is defined as the confirmed stringent complete response (sCR), complete response (CR), very good partial response (VGPR), and partial response (PR) as assessed by IMWG. The response is a binary term (e.g., 0 or 1, 1 = confirmed partial response (PR) or better; 0 = other response or NE).

If deemed appropriate and if data permit, dose/exposure - toxicity relationships between belantamab mafodotin dose/exposure and safety activity may be explored using above method. Safety activity will be assessed based on Dose-Limiting Toxicity (DLT). The response is also a binary term (e.g., 0 or 1, 1 = experienced DLT; 0 = non-experienced DLT).

If data permit, the effects of covariates (e.g., race, age, body weight) may also be explored.

The analyses will be based on the PK population, unless otherwise specified.

14.9.2. Pharmacokinetic / Pharmacodynamic Methodology

If deemed appropriate and if data permit, dose/exposure- safety/clinical activity relationships will be analysed using logistic regression. Generalized linear mixed model (GLMM) will be used which includes the terms of response of safety/clinical activity, dose intensity, duration of exposure in days, Cmax and AUC. If data permit, the effects of covariates (e.g., race, age, body weight) may also be included.

In order to determine which terms impact the response of safety/clinical activity significantly, the step-by-step method will be used to select the statistical significant terms.

The results of analyses based on the final model will be presented as estimated effect of selected terms, 2-sided 95% confidence intervals (CI), and associated p-values.

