2.3.3. Pharmacokinetics and Pharmacodynamics

The pharmacokinetics and pharmacodynamics of belantamab mafodotin (antibody-drug conjugate, including complex) with CCI), total monoclonal antibody (total mAb; including complex), and cys-mcMMAF were investigated in 291 participants with RRMM following IV administration at doses from 0.03 to 4.6 mg/kg Q3W in Study BMA117159 (n=73) and at doses of 2.5 or 3.4 mg/kg Q3W in Study 205678 (n=218).

Maximum concentrations (Cmax) of belantamab mafodotin and total monoclonal antibody were observed at or shortly after the end of infusion (EOI), while cys-mcMMAF Cmax values were generally observed on Day 2. On a molar basis, plasma concentrations of cys-mcMMAF were <1% of belantamab mafodotin concentrations. There was limited accumulation (less than 2-fold) of belantamab mafodotin or cys-mcMMAF during subsequent cycles.

Belantamab mafodotin pharmacokinetics were well described by a linear, two-compartment population model, with a time-varying decrease in clearance in a population

pharmacokinetic analysis. At Cycle 1, belantamab mafodotin had a systemic clearance of 0.92 L/day, steady-state volume of distribution of 11 L, and an elimination half-life of 12 days in participants with RRMM in Study 205678. Over time, clearance was reduced by 28%, resulting in an elimination half-life of 14 days. The time to 50% change in clearance was approximately 50 days.

No clinically significant differences in the pharmacokinetics of belantamab mafodotin or cys-mcMMAF were observed based on age (34 to 89 years), sex, race (African American/Black and White), body weight (42 to 130 kg), mild or moderate renal impairment (eGFR \geq 30 ml/min/1.73m²) or mild hepatic impairment (NCI-ODWG classification). Higher serum levels of β_2 -microglobulin, IgG, and column and lower levels of albumin are associated with more advanced multiple myeloma or a higher multiple myeloma disease burden. Higher baseline IgG and levels, and lower baseline albumin levels were associated with higher belantamab mafodotin clearance leading to lower average and trough concentrations (Ctau) of belantamab mafodotin. Higher baseline IgG and levels were associated with higher cys-mcMMAF central volume of distribution leading to lower cys-mcMMAF Cmax.

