4.1.2. Dose-Limiting Toxicity

The DLT observation window will be 21 days (1 cycle). Any participant that received at least 1 dose of belantamab mafodotin will be evaluated for DLTs using NCI-CTCAE Version 5.0 [NCI, 2017]. If participants prematurely discontinue for reasons other than toxicity but prior to completion of DLT observation period, additional participants may be enrolled as replacement participants at the discretion of the Sponsor in consultation with the investigator.

An event will be considered a DLT if its relationship to the investigational agent cannot be ruled out, occurs within the DLT reporting period and meets 1 of the following criteria:

- a. Any Grade 3 or greater non-hematologic toxicity as described in NCI-CTCAE Version 5.0 [NCI, 2017], other than corneal events:
- Persists for >48 hours despite supportive treatment
- Leads to hospitalization
- b. Haematologic toxicity:
- Grade 3 or greater febrile neutropenia lasting >48 hours despite adequate treatment:
 - Grade 3 CCI
 Grade 4 CCI
 CCI This section contained Clinical Outcome Assessment data collection questionnaires or indices, which are protected by third party copyright laws and therefore have been excluded.
- Grade 4 thrombocytopenia
 CCI
 CCI
- c. Grade 4 per the modified corneal grading scale provided in Table 7.
- d. Liver toxicity meeting pre-specified GSK liver stopping criteria as outlined in Section 7.1.1.

A participant who develops a DLT will be allowed to continue study treatment if the toxicity did not meet pre-defined stopping criteria (Section 7.1)and recovered to Grade ≤1 within 14 days or after a longer recovery period if the investigator and medical monitor agree that for a given participant the potential benefits may outweigh the risks.

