14.6.2. Study Population

Age

 Age will be calculated based on the date of first dose. Only year of birth is collected on the eCRF, therefore day and month of birth are imputed as '30JUN' in order to derive age. Birth date will be presented in listings as 'YYYY'.
Body Mass Index (BMI)

 Calculated as Weight (kg) / [Height (m)²]
Extent of Exposure

 Number of days of exposure to study drug will be calculated based on the formula: Duration of Exposure in Days = min(Last infusionDate+20, Death date) – First infusion Date + 1 Participants who were enrolled but did not report a treatment start date will be categorised as having zero days of exposure. The cumulative dose will be based on the formula: Cumulative Dose (mg/kg) = Sum of Dose at Each Cycle Dose intensity will be calculated based on the formula: Dose intensity (mg/kg/3 week) = Cumulative Dose/((last infusion date – first infusion date + 21)/21)

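### The exploratory exposure-response model in SAP 14.9 explains response and Cycle 1 DLT with duration and dose intensity, which accrue largely after those outcomes and are altered by them

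*SAP*

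**What the plan says.** SAP 14.9.2 plans a logistic (generalised linear mixed) model whose exposure terms are "dose intensity, duration of exposure in days, Cmax and AUC", with optional covariates. For choosing terms it says "the step-by-step method will be used to select the statistical significant terms", and it then reports effects, 95% confidence intervals and p-values from the selected model.

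SAP 14.9.1 gives two binary outcomes:
- **Response**, coded "1 = confirmed partial response (PR) or better; 0 = other response or NE".
- **Toxicity**: "Safety activity will be assessed based on Dose-Limiting Toxicity (DLT").

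The only definitions of the two dosing-history terms are in SAP 14.6.2. Duration begins "Duration of Exposure in Days = min(Last infusionDate+20, Death date") and subtracts the first infusion date, plus one day. Dose intensity begins "Dose intensity (mg/kg/3 week) = Cumulative Dose/((last infusion date" and divides by the whole first-to-last-infusion span in three-week units. Neither 14.6.2 nor 14.9 states a landmark, a Cycle 1 restriction or a time-varying form.

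On timing, Protocol 4.1.2 states: "The DLT observation window will be 21 days (1 cycle"). Protocol 6.1.1 and 7.1 continue treatment until progression or unacceptable toxicity, and Protocol 6.6 allows reductions and delays for toxicity.

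**The concern.** An explanatory term should be settled before the outcome it explains. Here the order is largely reversed.

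- **Response.** A participant who responds tends to progress later and so stays on drug longer. One who progresses at the first assessment cannot have a long duration. Long duration is then mostly a result of response, yet the model would present it as a driver.
- **DLT.** Everything in either term after Day 21 accrues once the DLT window has closed, and the DLT itself can change later dosing.

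Selection by p-value favours the strongest association, which in the response model is the reverse-caused one. A reported effect of longer exposure on response would look like evidence about exposure while only restating that responders are treated for longer.

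**Working it through.** The plan states no sample size, power or error rate for this analysis, so there is no figure of its own to reproduce.

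**1. Timing of response.** Assessments are every 3 weeks from Cycle 2 Day 1 (Schedule of Activities), and confirmation needs two consecutive assessments (SAP 7.1). The earliest confirmation is therefore about Cycle 3 Day 1, by when a participant has usually had at least two infusions: duration (21 + 20) + 1 = 42 days. Someone who progresses at Cycle 2 Day 1 after one infusion has (0 + 20) + 1 = 21 days. Part of the link between duration and response is thus built in.

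**2. Dose intensity and DLT, by the SAP 14.6.2 formula.** These courses are illustrative, at a 2.5 mg/kg start with the 1.9 mg/kg step of Protocol Table 4.
- DLT, stops after one infusion: 2.5 / ((0 + 21)/21) = 2.50 mg/kg/3 weeks.
- DLT, four infusions on schedule, reduced after the first: (2.5 + 3 × 1.9) / ((63 + 21)/21) = 8.2/4 = 2.05.
- No DLT, four full infusions on schedule: 10/4 = 2.50.
- No DLT, four full infusions with one 21-day delay: 10 / ((84 + 21)/21) = 10/5 = 2.00.

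Stopping gives the highest value possible at that dose, and reduction gives a low one. The association can go either way, depending on what happens after the DLT.

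**3. Simulation with no true exposure effect.**
- *From Protocol 2.3:* response 31%, median duration of response 11.0 months, median PFS 2.8 months (2.75 obtained), any reduction 32% and any delay 51% at 2.5 mg/kg.
- *Assumed:* per-cycle reduction chance 5-10% and delay chance 10-20%, giving any reduction in 27-40% and any delay in 45-62%; DLT rate 5-15%; share stopping after a DLT 0, 30 or 100%; forward selection by likelihood ratio with entry at 0.05 (the SAP gives no level). The mixed model's random effect was not simulated.
- *Sizes:* n = 12, this study's maximum (Protocol 4.1); and n = 230, that is 218 from Study 205678 (Protocol 2.3.3) plus 12, as an illustrative pool.

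Response model: median duration came out at 378 days in responders and 42-63 in non-responders. Mean dose intensity was 1.75-2.02 and 2.29-2.38 mg/kg/3 weeks respectively.

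| Selected under the null | n = 230 | n = 12 |
|---|---|---|
| Duration | 100% | 72-73% |
| Dose intensity | 6-9% | 21% |
| Any of the four terms | 100% | 90-91% |
| Any term, Cmax and AUC only | 10-14% | 15-16% |

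DLT model, n = 230: any term was selected in 28-100% of runs, falling to 4-10% with Cmax and AUC only. The mean correlation of DLT with dose intensity was -0.09 to -0.16 when nobody stopped after a DLT, about -0.02 when 30% stopped, and +0.18 to +0.30 when all stopped.

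**4. Multiplicity alone.** For independent null terms at 0.05: 1 - 0.95^4 = 18.5% for the four exposure terms, and 1 - 0.95^7 = 30.2% with race, age and weight added.

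**The case against.** The strongest reply is that this analysis may never be run from this SAP. SAP 14.9 applies only if deemed appropriate and if data permit. SAP 11.1 sends the details to a separate RAP and the results to a separate report, and SAP 14.12.16-14.12.17 list no PK/PD tables or figures. That stands, and it limits the weight of the point. It does not clear the text: the conditions govern whether the model is fitted, while 14.9.2 says how. If a separate RAP governs, the appendix should say so.

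A reader might infer more than the documents support:
- **That higher dose intensity would appear to protect against DLT.** This needs most participants with a DLT to continue at reduced doses. With enough stopping, the sign reverses.
- **That both terms would be selected for response.** Once duration was in the model, dose intensity entered in only 6-9% of runs at n = 230.
- **That a DLT model will be reported.** The study enrols up to 12 evaluable participants, and Protocol 4.2 reports no DLTs in the first-in-human study, so there may be too few events.
- **That disease-burden covariates are excluded.** The covariates in 14.9 are given as examples. Protocol 2.3.3 says "Higher baseline IgG and levels, and lower baseline albumin levels were associated with higher belantamab mafodotin clearance" (the text has a gap after IgG), which is a reason to name them, not proof that they are omitted.
- **That Cmax and AUC share the fault.** In this study they are in effect Cycle 1 measures: Protocol 9.4.10 lists them after single dose only, and SAP 10.1.1 bars Cmax where only predose and end-of-infusion samples exist. But 14.9 does not say so, and the overseas data may differ.
- **That dose choice here depends on the model.** Escalation follows the 3+3 rules and the Dose Escalation Committee, and no primary or secondary endpoint uses this model.

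It is also fair to say that the simulation builds in longer treatment for responders. It shows the direction and near-certainty of the artefact at a pooled size, not an exact rate.

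**Conclusion.** Wrong as written, within a conditional exploratory analysis. If 14.9.2 were followed literally, the response model would almost certainly report a positive duration effect at a pooled size, whether or not exposure matters. The 100% selection at n = 230 rests on the calibration and assumptions above, but the mechanism follows from the definition of duration and treatment to progression alone. For DLT the bias has no predictable direction, and the model may not be fittable. Stepwise selection adds multiplicity and unadjusted p-values; it is a secondary fault. The primary and secondary descriptive analyses are untouched.

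**What to change.** In SAP 14.9.1-14.9.2:

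1. Remove whole-treatment duration and dose intensity as explanatory terms.
2. Use exposure fixed before the outcome: Cycle 1 Cmax, AUC and Ctrough. For response, use Cycle 1 exposure or exposure up to a stated landmark.
3. State that Cmax and AUC are Cycle 1 values, in the pooled data as well.
4. Pre-specify the model terms instead of selecting them by p-value, preferably with baseline albumin and IgG among the covariates. Keep the estimates and confidence intervals already planned.
5. Reconcile 14.9 with SAP 11.1. State whether the separate RAP governs, and settle the toxicity outcome: 11.1 names corneal events and AESIs, whereas 14.9.1 names only DLT.

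The cost is SAP wording. Cycle 1 PK, albumin and IgG are already collected, so no new data are needed. In the simulation, leaving only Cmax and AUC cut false selection at n = 230 from 100% to 10-14% for response; what remains is ordinary selection error, which item 4 addresses.

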14.10. Appendix 10: Pharmacodynamic Biomarkers and Exploratory Response Prediction Biomarkers

CCI

14.11. Appendix 11: Abbreviations & Trade Marks

14.11.1. Abbreviations

Abbreviation	Description
ADA	Anti-drug antibodies
ADC	Antibody drug conjugate
AE	Adverse Event
AUC	Area under the curve
BCMA	B-cell maturation antigen
BM	Bone marrow
BNP	B-type natriuretic peptide
BP	Blood Pressure
C1D1	Cycle 1 Day 1
CDISC	Clinical Data Interchange Standards Consortium
CI	Confidence interval
CK	Creatine kinase
CL	Clearance
C _{max}	Maximum observed concentration
CR	Complete response
CRF	Case Report Form
CRP	C-reactive protein
CSR	Clinical study report
CT	Computed tomography
Ctrough	Trough plasma concentration after repeat dose
CV	Coefficient of variation
DLT	Dose limiting toxicities
DP's	Decimal Places
ECG	Electrocardiogram
ECHO	Echocardiogram
ECOG	Eastern Cooperative Oncology Group
EOI	End of Infusion
eCRF	Electronic case report form
eGFR	Estimated glomerular filtration rate
EOT	End of treatment
FISH	Fluorescence in situ hybridization
FLC	Free light chain
FSH	Follicle stimulating hormone
GFR	Glomerular filtration rate
GSK	GlaxoSmithKline
HCV	Hepatitis C virus
HR	Heart rate
ICH	International Conference on Harmonization
IDSL	Integrated Data Standards Library (GSK Standards Library)
IHC	Immunohistochemistry
IgA	Immunglobulin A

Abbreviation	Description
IgD	Immunoglobulin D
IgE	Immunoglobulin E
IgG	Immunoglobulin G
IgM	Immunoglobulin M
IMWG	International Myeloma Working Group
IV	Intravenous
LC	Light chain
LVEF	Left ventricular ejection fraction
MDRD	Modified diet in renal disease
MMAF	Monomethyl auristatin-F
CCI	
MRI	Magnetic resonance imaging
NE	Not Evaluable
ORR	Objective Response Rate
OSDI	Ocular Surface Disease Index
PD	Progressive disease
PDMP	Protocol Deviation Management Plan
PET	Positron Emission Tomography
PK	Pharmacokinetics
PR	Partial response
Q3W	Once every 3 weeks
QID	Four times a day
QTc	Corrected QT interval (ECG)
QTcF	Corrected QT interval Fridericia
RAP	Reporting and Analysis Plan
RNA	Ribonucleic acid
RRMM	Relapsed / refractory multiple myeloma
RTF	Rich Text Format
SAC	Statistical Analysis Complete
SAE	Serious adverse event
sCR	Stringent Complete Response
SCT	Stem cell transplant
SoA	Schedule of activities
SOI	Start of infusion
SOP	Standard operating procedure
SPD	Sum of the products of the maximal perpendicular diameters of measured lesions
SPEP	Serum Protein Electrophoresis
SRM	Study Reference Manual
t _{1/2}	Terminal phase half-life
T _{max}	Time of maximum observed concentration
UPEP	Urine protein electrophoresis
V	Volume of distribution
VGPR	Very good partial response

14.11.2. Trademarks

Trademarks of the GlaxoSmithKline Group of Companies
HARP

Trademarks not owned by the GlaxoSmithKline Group of Companies
SAS
WinNonlin

14.12. Appendix 12: List of Data Displays

All data displays will use the term “subject” rather than “participant” in accordance with CDSIC and GSK Statistical Display Standards.

14.12.1. Data Display Numbering

The following numbering will be applied for RAP generated displays:

Section	Tables	Figures
Study Population	1.010 to 1.xxx	1.010 to 1.xxx
Efficacy	2.010 to 2.xxx	2.010 to 2.xxx
Dose Limiting Toxicity	3.010 to 3.xxx	3.010 to 3.xxx
Safety	4.010 to 4.xxx	4.010 to 4.xxx
Immunogenicity	5.010 to 5.xxx	5.010 to 5.xxx
Pharmacokinetic / Biomarker	6.010 to 6.xxx	6.010 to 6.xxx
Section	Listings	
ICH Listings	1.010 to xxx	
Other Listings	30.010 to 30.xxx	

14.12.2. Mock Example Shell Referencing

Non IDSL specifications will be referenced as indicated and if required example mock-up displays provided in [Appendix 13: Example Mock Shells for Data Displays](#).

Section	Figure	Table	Listing
Study Population	POP_Fn	POP_Tn	POP_Ln
Efficacy	EFF_Fn	EFF_Tn	EFF_Ln
Dose Limiting Toxicity	DLT_Fn	DLT_Tn	DLT_Ln
Safety	SAFE_Fn	SAFE_Tn	SAFE_Ln
Immunogenicity	ADA_Fn	ADA_Tn	ADA_Ln
Pharmacokinetic	PK_Fn	PK_Tn	PK_Ln
Pharmacokinetic / Pharmacodynamic	PKPD_Fn	PKPD_Tn	PK/PD_Ln
CCI			

NOTES:

- Non-Standard displays are indicated in the ‘GSK Statistical Display Standard / Example Shell’ or ‘Programming Notes’ column as [Non-Standard] + Reference.’

14.12.3. Deliverables

Delivery [Priority] [1]	Description
SAC [1]	Final Statistical Analysis Complete

NOTES:

- Indicates priority (i.e. order) in which displays will be generated for the reporting effort

14.12.4. Study Population Tables

Study Population Tables					
No.	Population	GSK Standard / Example Shell	Title	Programming Notes	Deliverable [Priority]
Subject Disposition					
1.010	All Treated	ES8	Summary of Subject Status and Reason for Study Withdrawal		SAC [1]
1.020	Screened	ES6	Summary of Screening Status and Screening Failures		SAC [1]
1.030	All Treated	SD1	Summary of Treatment Status and Reasons for Discontinuation of Study Treatment		SAC [1]
Protocol Deviation					
1.040	All Treated	DV1	Summary of Important Protocol Deviations		SAC [1]
Population Analysed					
1.050	Screened	SP1	Summary of Study Populations		SAC [1]
Demographic and Baseline Characteristics					
1.060	All Treated	DM1	Summary of Demographic Characteristics		SAC [1]
Disease Characteristics					
1.070	All Treated	DC2	Summary of Disease Characteristics		SAC [1]
1.080	All Treated	POP_T1	Summary of Genetic Characteristics and Cytogenetics Risk at Screening		SAC [1]
Medical Conditions					
1.090	All Treated	MH1	Summary of Current Medical Conditions		SAC [1]
Prior and Follow-Up Anti-Cancer Therapy					

Study Population Tables					
No.	Population	GSK Standard / Example Shell	Title	Programming Notes	Deliverable [Priority]
1.100	All Treated	POP_T3	Summary of Prior Anti-Cancer Therapy by Drug Class of Agents		SAC [1]
1.110	All Treated	POP_T4	Summary of Subjects Refractory to Prior Anti-Cancer Therapy by Drug Class		SAC [1]
Extent of Exposure					
1.120	All Treated	EX1 / EX5	Summary of Exposure to Belantamab Mafodotin		SAC [1]
1.130	All Treated	OEX6	Summary of Dose Reductions of Belantamab Mafodotin		SAC [1]
1.140	All Treated	OEX6	Summary of Dose Delays of Belantamab Mafodotin		SAC [1]
1.150	All Treated	Non-Standard	Summary of Dose Modifications of Belantamab Mafodotin		SAC [1]
Prior and Concomitant Medications					
1.160	All Treated	CM8	Summary of Concomitant Medications		SAC [1]
1.170	All Treated	CM8	Summary of Blood Products		SAC [1]
1.180	All Treated	CM8	Summary of Blood Supportive Care Products		SAC [1]

14.12.5. Study Population Figures

No figures of study population analysis.

14.12.6. Efficacy Tables

Efficacy: Tables					
No.	Population	GSK Standard / Example Shell	Title	Programming Notes	Deliverable [Priority]
Response					
2.010	All Treated	Non-Standard	Summary of Objective Response Rate		SAC [1]
Time-to Event Endpoint					
2.020	All Treated	TTE1a	Summary of Duration of Response		SAC [1]
CCI					

